### **Echocardiogram**

For Echocardiogram, summary statistics for the baseline will be provided for:

- Left atrium
- Aortic root
- LV septum
- LV posterior wall

- LV diastolic diameter
- LV systolic diameter
- LV ejection
- RV free wall thickness
- Quantitative LV end systolic volumes
- Quantitative LV end diastolic volumes
- Transmitral E wave peak velocity
- E wave deceleration time
- Transmitral A wave Peak velocity
- Peak tricuspid regurgitation velocity
- Derived peak pulmonary artery systolic pressure
- Septal and Lateral Peak E, A, S
- Stroke volume
- Cardiac output

Also for the following parameters corresponding to Echocardiogram, summaries will be provided at baseline:

- Value abnormalities
- Types of value abnormalities
- Respiratory variation
- Sparkling

Echocardiogram summaries will be performed for the following sets: tafamidis untreated set with predominantly cardiac or mixed phenotype at enrollment, tafamidis treated set with predominantly cardiac or mixed phenotype at enrollment, CCI [REDACTED] and either predominantly cardiac or mixed phenotype at enrollment, tafamidis treated set for patients who switched from predominantly neurologic to mixed phenotype and tafamidis untreated set for patients who switched from predominantly neurologic to mixed phenotype.

*Note: For all the above safety events (Concomitant medications, hospitalization, AE/SAE, Deaths, Laboratory, Vitals and ECG) all events collected till last tafamidis dosing date +28 days will be summarized for the tafamidis treated set and its associated sub-sets.*

CCI [REDACTED]  
[REDACTED]  
[REDACTED]  
[REDACTED]  
[REDACTED]  
[REDACTED]

PFIZER CONFIDENTIAL

CCI [Redacted]

CCI [Redacted]

[Redacted]

[Redacted]

[Redacted]

[Redacted]

[Redacted]

[Redacted]

[Redacted]

[Redacted]

PFIZER CONFIDENTIAL

[Redacted]

CCI [Redacted]

[Redacted]

CCI [Redacted]

[Redacted]

- [Redacted]
- [Redacted]
- [Redacted]
- [Redacted]
- [Redacted]
- [Redacted]
- [Redacted]
- [Redacted]
- [Redacted]
- [Redacted]
- [Redacted]

[Redacted]

CCI [Redacted]

[Redacted]

[Redacted]

CCI [REDACTED]

[REDACTED]  
[REDACTED]  
[REDACTED]

[REDACTED]  
[REDACTED]

[REDACTED]

[REDACTED]  
[REDACTED]  
[REDACTED]

[REDACTED]

[REDACTED]  
[REDACTED]  
[REDACTED]

[REDACTED]

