### **11.6.1. Exposure During Pregnancy**

1. An exposure during pregnancy (EDP) occurs if a female becomes, or is found to be, pregnant either while receiving or having been directly exposed to (eg, environmental exposure) tafamidis, or the female becomes, or is found to be, pregnant after discontinuing and/or being directly exposed to tafamidis (maternal exposure).
2. An example of environmental exposure would be a case involving direct contact with a Pfizer product in a pregnant woman (eg, a nurse reports that she is pregnant and has been exposed to chemotherapeutic products).

As a general rule, prospective and retrospective EDP reports from any source are reportable irrespective of the presence of an associated AE and the procedures for SAE reporting should be followed.

If a study participant becomes, or is found to be, pregnant during the study participant's treatment with tafamidis, this information must be submitted to Pfizer, irrespective of whether an adverse event has occurred, using the NIS AEM Report Form and the EDP Supplemental Form, and through the Tafamidis Enhanced Surveillance for Pregnancy Outcomes (TESPO). Reporting to TESPO for women exposed to tafamidis will also include a 6-month and 12-month post-birth follow-up questionnaire regarding developmental milestones.

In addition, the information regarding environmental exposure to tafamidis in a pregnant woman (eg, a patient reports that she is pregnant and has been exposed to a cytotoxic product by inhalation or spillage) must be submitted using the NIS AEM Report Form and the EDP supplemental form. This must be done irrespective of whether an AE has occurred.

Information submitted should include the anticipated date of delivery (see below for information related to termination of pregnancy).

Follow-up is conducted to obtain general information on the pregnancy; in addition, follow-up is conducted to obtain information on EDP outcome for all EDP reports with pregnancy outcome unknown. A pregnancy is followed until completion or until pregnancy termination (eg, induced abortion) and Pfizer is notified of the outcome. This information is provided as a follow up to the initial EDP report.

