**Table 1 Summary of ongoing tafamidis safety concerns to be addressed in THAOS**

Level of Risk or Missing Information	Specific Concerns
Important potential risks	Hepatotoxicity Reproductive and developmental toxicity and lactation Changes in thyroid function, particularly in pregnant women
Important missing information	Safety and efficacy in patients with ATTR-PN variants other than Val30Met (B3461029 substudy) CCI █ Patients with severe hepatic impairment

Note: The important identified risks (Urinary tract infections, Diarrhea, Upper abdominal pain and Vaginal infections); important potential risks (Hypersensitivity reactions); and missing information (Safety and efficacy in elderly patients and Longer-term safety) have been removed from the list of ongoing safety concerns from the tafamidis EU Risk Management Plan (RMP) Update (v 9.3), approved on 17 February 2020 and therefore will not be addressed in the final clinical study report (CSR) for THAOS.

All AE/SAE data will be collected for patients treated with commercially available tafamidis; patients receiving tafamidis as part of their participation in an open-label clinical study will have AE/SAE data collection through the open-label clinical study; reporting of Health Events of Interest will be available for patients not treated with tafamidis.

All visits are intended to be outpatient visits. Table 2 presents the data collected throughout a patient's participation in THAOS per the case report form (CRF). All assessments listed in Table 2 are recommended, but not required and will be determined by the investigator.

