## 5.3 TAFAMIDIS TREATED

The tafamidis treated set will include the following:

[figure not shown]
- All available data from the enrollment date until final treatment discontinuation of tafamidis or end of follow-up in THAOS (whichever is earlier) for patients who have been enrolled in THAOS, signed the informed consent and who were on tafamidis treatment on or prior to the date of enrollment in THAOS.
- All available data from first dose of tafamidis until final treatment discontinuation of tafamidis or end of follow-up in THAOS (whichever is earlier) for patients who were not on tafamidis at the time of enrollment in THAOS but subsequently initiated treatment with tafamidis.

Note: A patient can be considered part of both the tafamidis untreated and tafamidis treated sets if the patient initiated treatment with tafamidis after beginning participation in THAOS.

The below schematic will help to better understand the patient population to be analysed:

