### Adverse Events & Serious Adverse Events

All adverse events will be coded according to the latest Medical Dictionary for Regulatory Activities (MedDRA) version at the time of analysis.

Adverse events (all causality and treatment-related) will be summarized by severity and starting dose using the tafamidis treated set by phenotype at enrollment and overall, CCI [REDACTED] and either predominantly cardiac or mixed phenotype at enrollment, tafamidis treated set for patients who had severe hepatic impairment at baseline, tafamidis treated set by liver transplantation status (liver transplant prior to first dose of tafamidis/liver transplant after the first dose of tafamidis/no liver transplant).

Separate summaries will be provided for all AEs, treatment related AEs, all SAEs, treatment related SAEs, AEs leading to dose reduction, AEs leading to withdrawal of tafamidis (temporarily or permanently, or delayed) and AEs leading to tafamidis dose interruptions.

Listings will be provided for adverse events corresponding to all enrolled patients and for patients with off-label usage of tafamidis. A separate listing of SAEs will also be provided for tafamidis treated set.

The following AE summary tables will be provided corresponding to some of the important potential risks using the tafamidis treated set.

- For **hepatotoxicity** using the search criteria: MedDRA SMQ (Standardized MedDRA Query) [Broad and narrow] Drug related hepatic disorders – comprehensive search. The derivations and conventions related to the search criteria will follow the programming specifications done in the Periodic Safety Update Report (PSUR) 12 for tafamidis.
- For **reproductive and developmental toxicity and lactation**:
  - MedDRA SMQ (Broad and narrow): Congenital, familial and genetic disorders; Foetal disorders; Neonatal disorders, Neonatal exposures via breast milk.
  - MedDRA Preferred terms (PTs): Exposure during pregnancy, Exposure via father, Foetal exposure during delivery, Foetal exposure during pregnancy, Foetal exposure timing unspecified, Maternal exposure before pregnancy, Maternal exposure during delivery, Maternal exposure during pregnancy, Maternal exposure timing unspecified, Drug exposure before

- pregnancy, Exposure via breastmilk, Maternal drug affecting foetus, Maternal exposure during breastfeeding
- The derivations and conventions related to the search criteria will follow the programming specifications done in the PSUR 12 for tafamidis.

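### Pregnancy, foetal, neonatal and lactation events more than 28 days after the final tafamidis dose are left out of the reproductive-toxicity summary table, although the protocol follows pregnancies to outcome

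*SAP*

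**What the plan says.** SAP Table 1 (section 2.1) lists "Reproductive and developmental toxicity and lactation" among three important potential risks still to be addressed. Section 8.2.6 (Adverse Events & Serious Adverse Events) gives the output: "The following AE summary tables will be provided corresponding to some of the important potential risks using the tafamidis treated set". For this risk the search covers "Congenital, familial and genetic disorders; Foetal disorders; Neonatal disorders, Neonatal exposures via breast milk", together with a list of exposure preferred terms that includes maternal exposure before pregnancy.

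Two rules then limit the dates:

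- The note at the end of 8.2.6 begins "For all the above safety events (Concomitant medications, hospitalization, AE/SAE, Deaths, Laboratory, Vitals and ECG" and sets the limit: "all events collected till last tafamidis dosing date +28 days will be summarized for the tafamidis treated set and its associated sub-sets". AE/SAE data are named, and pregnancy is not excepted.
- Section 5.3 defines the treated set for women who start after enrolment as "All available data from first dose of tafamidis until final treatment discontinuation of tafamidis or end of follow-up in THAOS (whichever is earlier". The same end applies to women already on tafamidis at enrolment. Only the final discontinuation counts.

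The protocol is wider. Section 11.2 runs safety reporting to the end of the observation period, with 28 days after the last dose as the least it must include. Section 11.6.1 counts as an exposure a pregnancy that begins or is found after tafamidis has been discontinued. It then says: "A pregnancy is followed until completion or until pregnancy termination (eg, induced abortion) and Pfizer is notified of the outcome". Adverse pregnancy outcomes follow SAE procedures (11.6.1), and every SAE is recorded in the THAOS data record (11.1).

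**The concern.** A 28-day window after last dose is a common choice for ordinary treatment-emergent events, but it does not fit this risk. The outcomes that the table searches for can arise months after the exposure that might have caused them. If a woman's final dose falls early in pregnancy, the table can keep the exposure term and an early loss close to that dose. It drops an anomaly found at birth, a neonatal event or a lactation event. A table with few or no developmental events could then reflect the date filter and say little about the drug. The final report serves a post-authorisation commitment to the EMA, and this is one of the risks it is meant to address.

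**Working it through.** The plan gives no figure to reproduce: no count of pregnancies, no expected rate and no gestational timing. The check has two parts.

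**1. Can a late event enter any AE summary?** Take an event dated more than 28 days after the final dose.

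| Place in the SAP | Is the event summarised? |
|---|---|
| 8.2.6 closing note, treated set | No, it is past last dose + 28 days |
| 5.3, treated set | No, data end at final discontinuation |
| 5.2, untreated set | No, data after discontinuation are excluded |
| 8.2.8 summary grid, AE/SAE row | Only treated columns are marked, none for all enrolled or untreated |
| 8.2.6, AE listing for all enrolled patients | Possibly listed, as no cut-off is stated, but not tabulated |

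So no AE summary table picks the event up. By the same rule, the term for maternal exposure before pregnancy cannot be counted when it is dated more than 28 days after the last dose, although it is on the search list.

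The two treated-set rules also disagree. An event on days 1 to 28 after the final dose is kept by the 8.2.6 note and lost under 5.3.

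**2. How far outside the window do birth outcomes fall?** Gestational weeks are my assumption. The 28 days come from the 8.2.6 note.

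Days from final dose to birth = 7 × (week of birth − week of final dose). Days past the cut = that figure − 28.

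| Birth (week) | Final dose (week) | Days to birth | Days past the cut |
|---|---|---|---|
| 40 | 5 | 7 × 35 = 245 | 217 |
| 40 | 8 | 7 × 32 = 224 | 196 |
| 40 | 12 | 7 × 28 = 196 | 168 |
| 37 | 12 | 7 × 25 = 175 | 147 |
| 41 | 4 | 7 × 37 = 259 | 231 |

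Across a final dose at week 4 to 12 and birth at week 37 to 41, an event at birth is 147 to 231 days past the cut.

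An event at birth falls inside the window only if the final dose is no more than 4 weeks earlier: at or after week 33, 36 or 37 for birth at week 37, 40 or 41. Even with a final dose at week 36 and birth at week 40 (day 28, just inside), the end of a 30-day neonatal month falls 28 + 30 − 28 = 30 days past the cut.

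**The case against.** A reader might infer that births and infant outcomes after a woman stops tafamidis never reach the table, or are lost to the study. The documents do not support that:

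- Under the 8.2.6 note, events up to 28 days after the last dose are kept.
- Only the final stop counts, so events during an interruption followed by a restart are kept.
- Exposure terms dated on treatment still enter, so the exposed pregnancy itself can be visible.
- A normal live birth is not among the search terms, so its absence is not a loss.
- The all-enrolled AE listing may show late cases.
- Adverse outcomes also go to the sponsor's safety function as SAEs, and pregnancies on treatment go to the tafamidis pregnancy surveillance programme (protocol 11.1 and 11.6.1).
- Annual regulatory reporting has separate analysis plans (SAP section 2).

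All of this stands. It confines the loss to one summary table in the final report.

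Two further objections carry some weight. The SAP refers the search conventions to the programming specifications of an earlier periodic safety report, which might deal with dating of pregnancy cases. The SAP cites them for the search criteria and states no separate window. The note also does not say whether onset date or collection date governs its limit. Both points are reasons to write the window down.

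A full analysis per exposed pregnancy would be a larger request than it looks. The 6- and 12-month infant questionnaires belong to the surveillance programme. The visible rows of SAP Table 2 show no pregnancy form or conception date, though some rows are redacted. Splitting a possibly small number of pregnancies could also trigger the SAP's own rule that subgroups under 10 get listings only.

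**Conclusion.** The point holds in this form: as written, adverse pregnancy, foetal, neonatal and lactation events dated more than 28 days after the final tafamidis dose are excluded from the reproductive-toxicity summary table, and no other AE summary takes them in. The SAP turns the protocol's minimum reporting period into a maximum for the one risk where later outcomes matter most.

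The distance past the window rests on the assumed gestational weeks. The exclusion rests only on the text, read with event date as the governing date. How many events are affected cannot be computed, because the documents give neither the number of exposed pregnancies nor when women stop. It would go too far to say that most anomalies are dropped or that the table is biased by a known amount.

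**What to change.** In SAP 8.2.6, exempt the reproductive and developmental toxicity and lactation table from the +28-day limit and from the 5.3 end at discontinuation. Let it count every matching AE/SAE term recorded in THAOS for women ever treated with tafamidis in THAOS, whatever the days since last dose. Flag each event as on treatment or within 28 days, or later.

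Keep +28 days for all other adverse events. Reconcile 5.3 with the 8.2.6 note, and state which date governs the limit.

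Report outcomes per exposed pregnancy, by timing of exposure, only if the data recorded in THAOS allow it.

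The cost is a sentence or two in the SAP and a different date filter with one flag for a single table. The basic change needs no new data collection, since the protocol already has SAEs recorded in THAOS. The downside is that a few events remote from dosing will enter the table, and the timing flag shows which they are.

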8.2.8 Summary of Analyses

Data	All enrolled	Untreated overall & by phenotype	Untreated predominantly neurologic/mixed	Untreated predominantly cardiac/mixed	Treated Overall and by phenotype	Treated predominantly neurologic/mixed	Treated predominantly cardiac/mixed	Treated by starting dose	[REDACTED]	[REDACTED]	Treated severe hepatic impaired at baseline	Patients not on tafamidis at the time of enrollment with a liver transplant prior to enrollment on THAOS	Patients not on tafamidis at the time of enrollment with a liver transplant after enrollment on THAOS	Patients not on tafamidis at the time of enrollment with no liver transplant	Treated with liver transplant prior to first dose of tafamidis in the study	Treated with liver transplant after first dose of tafamidis in the study	Treated with no liver transplant either prior to first dose of after first of tafamidis in the study	Treated with off-label usage	Untreated predominantly neurologic who become mixed	Untreated predominantly cardiac who become mixed	Treated predominantly neurologic who become mixed	Treated predominantly cardiac who become mixed
Disposition	x	x			x																	
Demography	x	x			x																	
Disease Characteristics	x	x			x																	
Misdiagnoses	x	x			x																	
Ongoing symptoms by A.T.T.R		x			x				x													
relatedness (definite/possibly related/unrelated)																						
Past symptoms by A.T.T.R		x			x																	
relatedness (definite/possibly related/unrelated)																						
New symptoms by A.T.T.R		x			x																	

PFIZER CONFIDENTIAL

CCI				x			x		x			x							x			x	
				x			x		x														
			x			x						x	x	x							x		x
Survival		x			x					x	x	x	x	x	x	x	x						
Exposure to Tafamidis					x			x		x	x				x	x	x						
Concomitant medications		x			x																		
Hospitalizations		x			x					x													
AE/SAE					x			x		x	x				x	x	x	x					
Death	x	x			x					x	x	x	x	x	x	x	x						
Labs – baseline and change from baseline		x			x			x															
Hy's Law					x			x															

Blood pressure – baseline and change from baseline	x	x			x															
ECG				x			x			x								x		x
ECHO				x			x			x								x		x
CCI		x			x															
[REDACTED]			x			x														
[REDACTED]			x			x														
[REDACTED]			x			x														
[REDACTED]				x			x		x									x		x
[REDACTED]				x			x													
Transplant		x			x															
[REDACTED]		x			x															

## 10 APPENDICES

### APPENDIX 1: LIST OF ABBREVIATIONS

CCI	
ADL	activities of daily living
AE	adverse events
ANCOVA	analysis of covariance
ATTR	Transthyretin amyloid protein
ATTR-CM	transthyretin amyloid cardiomyopathy
ATTR v	ATTR due to a variant
ATTR-PN	transthyretin amyloid polyneuropathy
ATTR wt	ATTR wild type
CHMP	Committee for Medicinal Products for Human Use
CI	Confidence interval
CRF	case report form
CSR	clinical study report
ECG	electrocardiogram
EMA	European Medicine Agency
CCI	
EU	European Union
GFR	glomerular filtration rate
GI	gastrointestinal
ICD	implantable cardiac defibrillator
ICF	informed consent form
CCI	
MedDRA	Medical Dictionary for Regulatory Activities
mg	milligram
MMRM	Mixed model repeated measures
CCI	
MRC	Medical Research Council
NI	Non-interventional
CCI	

PFIZER CONFIDENTIAL

CCI	
PASS	Post-Authorization Safety Study
PSUR	Periodic Safety Update Report
PT	Preferred term
QoL	Quality of Life
QTcF	corrected QT (Fridericia method)
RMP	Risk Management Plan
ROM	Range of Motion
SAE	serious adverse events
SAP	statistical analysis plan
SD	Standard deviation
SMQ	Standardized MedDRA Query
TFL	Tables, Figures and Listings
THAOS	The Transthyretin-Associated Amyloidosis Outcomes Survey
TQoL	Total quality of Life
TTR	Transthyretin
Val30Met	Substitution of methionine for valine at position 30
VAS	visual analogue scale

## APPENDIX 2: DATA DERIVATION DETAILS

### A1.1 Definition and use of visit windows in reporting

For All enrolled set and tafamidis untreated set (as well as the subgroups corresponding to untreated set), Day 1 will be the most recent available value collected either on or after the informed consent signed date. The study day will be calculated as follows:

Study day = assessment date – consent date

For the tafamidis treated set (as well as the subgroups corresponding to treated set), Day 1 will be the most recent available value collected either on or after the first dose of tafamidis received after enrollment in THAOS. The study day will be calculated as follows:

Study day = assessment date – date of first dose of tafamidis after enrollment in THAOS / consent date if patient was continuing taking tafamidis prior to enrollment (whichever is earlier) + 1

The following visit window will be applied, considering the absolute value of study day (absday):

Condition	Visit	Year
$\text{absday} < -365.25 \times 0.5$	-1	
$0 \leq \text{absday} \leq 365.25 \times 0.5$	0	
$365.25 \times 0.5 < \text{absday} \leq 365.25 \times 1.5$	1	1
$365.25 \times 1.5 < \text{absday} \leq 365.25 \times 2.5$	2	2
$365.25 \times 2.5 < \text{absday} \leq 365.25 \times 3.5$	3	3
$365.25 \times 3.5 < \text{absday} \leq 365.25 \times 4.5$	4	4
$365.25 \times 4.5 < \text{absday} \leq 365.25 \times 5.5$	5	5
$365.25 \times 5.5 < \text{absday} \leq 365.25 \times 6.5$	6	6
$365.25 \times 6.5 < \text{absday} \leq 365.25 \times 7.5$	7	7
$365.25 \times 7.5 < \text{absday} \leq 365.25 \times 8.5$	8	8
$365.25 \times 8.5 < \text{absday} \leq 365.25 \times 9.5$	9	9
$365.25 \times 9.5 < \text{absday} \leq 365.25 \times 10.5$	10	10
$365.25 \times 10.5 < \text{absday} \leq 365.25 \times 11.5$	11	11
$365.25 \times 11.5 < \text{absday} \leq 365.25 \times 12.5$	12	12

Note: If study day is missing, then visit will be considered as missing.

CCI [REDACTED]

	CCI [REDACTED]	[REDACTED]	[REDACTED] → [REDACTED]
CCI [REDACTED]	[REDACTED]	[REDACTED]	[REDACTED]
[REDACTED]	[REDACTED]	[REDACTED]	0 → 4 1 → 3.75 2 → 3.5 3 → 3.25 4 → 2 5 → 0
[REDACTED]	[REDACTED]	[REDACTED]	Present → [REDACTED] [REDACTED] → [REDACTED]
[REDACTED]	[REDACTED]	[REDACTED]	Normal → [REDACTED] Decreased → [REDACTED] Absent → [REDACTED]
CCI [REDACTED]	[REDACTED]	[REDACTED]	[REDACTED]

CCI	

• [REDACTED]

• [REDACTED]

• [REDACTED]

• [REDACTED]

• [REDACTED]

• [REDACTED]

• [REDACTED]

• [REDACTED]

	

• [REDACTED]

• [REDACTED]

• [REDACTED]

• [REDACTED]

• [REDACTED]

• [REDACTED]

• [REDACTED]

• [REDACTED]

	[REDACTED]
[REDACTED]	

• [REDACTED]

• [REDACTED]

	

• [REDACTED]

• [REDACTED]

	[REDACTED]
CCI	

• [REDACTED]

	

• [REDACTED]

• [REDACTED]

	[REDACTED]
[REDACTED]
